2. STUDY DESIGN

2.1 Study summary and flow diagram

POSED is a stand-alone open-label feasibility study. A single-centre, cluster-randomised multi-arm study will be performed to assess feasibility measures that would inform the design of a large-scale trial. This single-centred study will be hosted by South Central Ambulance Service, an NHS ambulance service in the south of England.

The population of interest is patients sustaining out-of-hospital cardiac arrest who, on assessment by an ambulance crew, display a shockable cardiac rhythm (VF or pulseless ventricular tachycardia (VT)). This may be the initial or subsequent rhythm.

Defibrillators will be randomised to deliver one of three shock strategies:

Group	First shock	Second shock	Subsequent shocks	Strategy
1	120	150	200	Escalating
2	150	200	200	Escalating
3	200	200	200	Fixed

The comparator groups have been selected as they represent current UK practice. Group 1 delivers shock energies according to manufacturer's current guidance. Group 2 delivers shock energies according to current practice at the study site, but this is anomalous to the other NHS ambulance services. Although none of the UK ambulance services currently employs the group 3 energies, equivalent energy settings, i.e. high-high-high, are employed using BTE waveform in a number of NHS ambulance services. Group 3 is representative of current practice in these ambulance services.

In preparation for this study, a small scoping exercise of paramedics was conducted within the proposed study site. The scoping exercise found that 70% of paramedics felt that the first shock should be >120J whilst 95% felt that an escalating regime should be used. Whilst holding opinions on shock strategy, the exercise revealed that 30% of paramedics did not know what energies their defibrillators were programmed to deliver. When asked about the acceptability of randomising the intervention, 95% indicated that they would be willing to take part in a study comparing fixed and escalating shock levels.

Each shock takes a fraction of a second to be delivered by the defibrillator to the patient's heart. Patients may require one or many shocks during the pre-hospital phase. The resuscitation attempt may last from 20 min to approximately 60 minutes depending on journey time to hospital. Study treatment ceases on the handover of care to the hospital team who will continue with their normal care from this point.

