2.3.3 Process outcomes

Process outcomes, including CPR metrics and resuscitation treatments, will be reported. These will be obtained from the defibrillator data downloads and electronic patient record. The following process outcomes will be recorded:

- Quality of CPR (chest compression rate, chest compression depth, chest compression fraction, pre-shock pause, post-shock pause)

- Number of shocks
- Advanced airway applied (% advanced airway applied and % supraglottic airway or endotracheal tube)
- Intravenous medicines administered (% cases where medicines administered and % adrenaline, amiodarone)
- Transported to hospital (% transported)

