2.8 Randomisation

2.8.1 Randomisation

Due to the time-critical nature of cardiac arrest, delay to shock delivery must be minimised. Any method of individual patient randomisation would necessarily incur a delay as the shock energy would need to be adjusted on the defibrillator. For this reason, randomisation will be on a cluster basis, the unit of randomisation being the defibrillator. Defibrillators are allocated to specific vehicles (ambulances or rapid response cars) and are not usually moved between vehicles as they are paired with the on-board electronic patient record tablet device. *The trial initially defined a cluster as a defibrillator, which as noted above, according to ambulance protocols, should remain co-located with a specific ambulance vehicle. During the conduct of the trial, it became evident that, on occasion, defibrillators became separated from their associated ambulance vehicles. As the Ambulance Service tracks vehicles rather than defibrillators it was only possible to track patients where the vehicle and defibrillator remained together. After careful consideration by the Sponsor, with input from the patient and public advisory group and approval from the Research Ethics Committee, the definition of a cluster was clarified as a defibrillator carried by its associated ambulance vehicle.* To minimise the risk of movement, defibrillator bags will be marked with the callsign of their allocated vehicle and display stickers reminding staff not to move them.

Defibrillators *on their associated ambulance vehicles* will be allocated to one of the three treatment groups in a 1: 1: 1 ratio. The randomisation schedule will be prepared by the study statistician and defibrillators shall be allocated to a treatment arm in a 1: 1: 1 ratio using simple randomisation. The statistician shall ensure that the sequence is not predictable based on vehicle type.

The experimental protocol ends after three shocks. In the event of a change of defibrillator during a patient care episode, normal trust policy will apply regarding shock energy escalation (i.e. second and subsequent shocks to be delivered at 200J).

At the point of device charging, staff will know which treatment they are delivering and so will not be blinded. Possible performance bias will be assessed by monitoring variables such as numbers of patients conveyed to hospital and not conveyed in each of the treatment arms.

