6.2.3.1 Summary of baseline data and flow of patients

Baseline comparability of the randomised groups will be assessed using the following variables:

- Age (median and range)
- Sex (% male)
- Location of arrest (% private residence/ public place/ other)
- Witnessed vs. unwitnessed event (% witnessed and % bystander/ EMS or other healthcare provider/ unwitnessed)
- Bystander CPR vs. no bystander CPR (of those not EMS-witnessed, % provided BCPR prior to EMS arrival)
- Type of initial rhythm (% in VF/pVT, PEA or asystole)
- Time from call to application of defibrillator (median and range)
- Aetiology of cardiac arrest (% cardiac vs. non-cardiac cause)

Flow of patients will be presented using a consort flow diagram (<http://www.consort-statement.org/>).

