6.6 Sub-groups

In relation to initial shock (VT/pVT) as our outcome, we will conduct sub-group analyses of:

1. Hospital handover (ROSC, CPR ongoing, not conveyed);
2. 30 days survival (died/alive);
3. Survival at discharge (died/alive).

We will assess the interaction of the treatment arm, with each of the sub-groups.

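### The only performance-bias indicator named in section 2.8.1, conveyance by arm, is decided after randomised shocks, so the raw count mixes shock effect with staff behaviour

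*Protocol*

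**What the plan says.** Section 2.8.1 states the problem openly: "At the point of device charging, staff will know which treatment they are delivering and so will not be blinded". Its remedy is to watch a set of variables for signs of performance bias, and the example it gives is "numbers of patients conveyed to hospital and not conveyed in each of the treatment arms". The list is open, but conveyance is its only member.

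Other parts of the protocol bear on what conveyance measures:

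- Section 2.1 places the randomised treatment across the whole pre-hospital phase: "Study treatment ceases on the handover of care to the hospital team".
- Section 2.3.3 lists conveyance as a process outcome, "Transported to hospital (% transported"), beside CPR metrics, "Quality of CPR (chest compression rate, chest compression depth, chest compression fraction, pre-shock pause, post-shock pause"), and beside airway and medicines.
- Section 6.6 records conveyance and circulatory status in one variable: "Hospital handover (ROSC, CPR ongoing, not conveyed").
- Section 2.9.2 compares delivered with allocated energy from the defibrillator download, and section 6.2.3.3 reports adherence for the first shock.

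The CPR, airway, medicines and adherence data are nowhere linked to the assessment of performance bias.

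**The concern.** A useful indicator of performance bias should respond to what staff do and not to whether the allocated shock worked. Conveyance responds to both. A patient whose circulation returns is a natural candidate for transport. One whose circulation does not return may be conveyed with CPR continuing or not conveyed at all, and that choice is open to staff belief. The raw count by arm adds the two together.

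A gap between arms may therefore be pure treatment effect, and equal counts may hide a treatment effect offset by different persistence. More patients would not cure this.

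The risk is not abstract here. In the scoping exercise in section 2.1, 70% of paramedics thought the first shock should exceed 120J and 95% favoured escalation, so groups 1 and 3 each run against majority opinion. The study is meant to inform a definitive trial, which would inherit the open-label design and whatever was concluded about it.

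**Working it through.** The protocol gives no figure for this check, so there is none to reproduce. What follows is an illustration.

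**Inputs**

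- Organised-rhythm rate, r: 36% and 25.7%. Section 1.2.2 reports these for an earlier randomised trial of escalating higher against fixed lower energy. That trial used stacked shocks, so the figures only give a plausible size of difference.
- Probability of conveyance with an organised rhythm, c1: 95-100%. Assumed.
- Probability of conveyance without one, c0: 20-80%. Assumed.
- Patients per arm: 30 (section 6.1).

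**Step 1. Identical staff behaviour, different shock success.**

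P(conveyed) = r × c1 + (1 − r) × c0, with the same c1 and c0 in both arms. The gap is (0.36 − 0.257) × (c1 − c0) = 0.103 × (c1 − c0).

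| c1 | c0 | Conveyed, r = 36% | Conveyed, r = 25.7% | Gap (points) |
|---|---|---|---|---|
| 1.00 | 0.20 | 48.8% | 40.6% | 8.2 |
| 1.00 | 0.40 | 61.6% | 55.4% | 6.2 |
| 1.00 | 0.60 | 74.4% | 70.3% | 4.1 |
| 1.00 | 0.80 | 87.2% | 85.1% | 2.1 |
| 0.95 | 0.20 | 47.0% | 39.3% | 7.7 |
| 0.95 | 0.40 | 59.8% | 54.1% | 5.7 |
| 0.95 | 0.60 | 72.6% | 69.0% | 3.6 |
| 0.95 | 0.80 | 85.4% | 83.9% | 1.5 |

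**Step 2. Same gap from behaviour alone.**

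Take c1 = 1.00, c0 = 0.40 and r = 25.7% in both arms, so there is no treatment effect. The 6.2-point gap reappears if staff in one arm convey non-responders more often by 0.0618 / (1 − 0.257) = 0.083, that is 8.3 points.

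**Step 3. A real effect hidden by behaviour.**

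Keep r = 36% and 25.7%. Conveyance is equal at 55.4% if staff in the better arm convey non-responders with probability (0.554 − 0.36) / (1 − 0.36) = 0.303 instead of 0.40. The count shows nothing, although shock success and staff behaviour both differ.

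**Step 4. Precision.**

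The 95% half-width for a difference between two arms of 30 is 1.96 × √(2p(1 − p)/30). This gives 25.3 points at p = 0.5, 24.8 at p = 0.6 and 20.2 at p = 0.8, ignoring clustering by defibrillator.

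Steps 1 to 3 carry the point: the raw count does not identify its own cause. Step 4 applies to any marker at this sample size.

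**The case against.** The strongest reply is that section 2.8.1 offers conveyance only as an example, sets no threshold or decision, and sits in a protocol that already collects CPR quality, adherence and handover status. How these are tabulated may be left to the analysis plan announced in section 6.2.3, which was not available for this review. The study plans no formal comparison (section 6.2.1) and assesses data for completeness rather than effectiveness (section 7.10). All of this stands and limits the consequence. It does not make the one named indicator suitable, and nothing in the protocol ties the better-suited data to this purpose.

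A reader might go further than the documents allow in four ways:

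- *That conveyance is the whole test, or a rule that declares bias.* The wording is open and speaks only of monitoring.
- *That each 10-point difference in ROSC moves conveyance by 10 points.* That needs nobody without ROSC to be conveyed. The handover category for continuing CPR shows that some are.
- *That the interval of about ±25 points counts against conveyance.* It comes from 30 patients per arm and would affect other markers too.
- *That conveyance should be discarded as evidence.* Persistence and the decision to transport are where unblinded belief could plausibly act, so dropping it would lose a signal.

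The reply is also right about very early markers. Staff see the energy on charging, so measures settled before then say little unless the crew already knows the vehicle's setting. "Time from call to application of defibrillator (median and range"), listed in section 6.2.3.1, is a baseline descriptor for that reason, not a performance marker.

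**Conclusion.** The point holds in a limited form. Conveyance is the only indicator named, it is decided after at least one randomised shock, and its raw count by arm can neither show nor exclude performance bias. Under the assumed conveyance rates, a difference of 36% against 25.7% in organised rhythm moves conveyance by about 1.5 to 8 points with identical staff behaviour.

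That conveyance depends on shock result is an inference from the timing of treatment and from the handover categories; the protocol does not say it in words. The size rests on assumed conveyance rates and on rhythm rates from a different shock regime. No stated conclusion or progression decision depends on this check. It is a cheap improvement to the evidence passed to a main trial, not a threat to the primary feasibility result.

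**What to change.** Amend the sentence in section 2.8.1 in two ways.

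1. Name markers of staff behaviour that arise once the energy is known but before the first shock's result is analysed, and report them by arm: manual change of the pre-set first energy; pre-shock and post-shock pause of the first shock; and compression rate, depth and fraction up to the first two-minute rhythm check. Because section 2.5 admits patients first shocked by a public-access device, define the first shock as the first from the study defibrillator.
2. Keep conveyance, but show it by arm within handover status (ROSC, CPR ongoing, not conveyed). State that the raw count alone neither shows nor excludes performance bias. State also that the breakdown by ROSC conditions on a post-randomisation variable and is descriptive only.

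The data are already planned for collection (sections 2.3.3, 2.9.2, 5.1 and 6.6). The cost is a changed sentence and one extra table. Cases without a defibrillator download drop out of the early markers, and with about 30 patients per arm all these comparisons will be imprecise, so the table should be read as description.

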2.8.2 Post-randomisation withdrawals, exclusions and Moves out of Region

The treatment allocation determines the energy levels of the first three shocks. Should the patient gain ROSC and then refrillation occurs, they will receive the next allocated energy level in the allocation.

Should a patient decline consent, the date on which this is communicated shall be recorded on the database and no further contact made. Any data gathered up to this point shall be retained unless the patient has expressly declined consent for this data.

Unless a participant explicitly withdraws their consent, they should be followed-up wherever possible and data collected as per the protocol until the end of the study.

The National Data Opt-Out will not apply to data for this study as only non-identifiable data will be transferred from the NHS to the university.

2.9 Study treatments / intervention

2.9.1 Study treatment(s) / intervention

All participants will receive standard resuscitation treatment according to current Resuscitation Council (UK) and JRCALC guidelines. These advise at least 150J for initial shock and the same or higher energy for subsequent shocks, or to follow defibrillator manufacturer's guidance. The exception to this is that defibrillation energies will be randomly allocated.

Qualitative sub-study participants shall be invited to attend a focus group session following their normal team meeting on Trust premises.

2.9.2 Compliance/contamination

It will be important to monitor adherence to treatment allocation. Treatment *delivery* will be compared to treatment *allocation*. Should the energy delivery differ from that which was allocated, this shall be deemed non-compliance and will be documented. Treatment delivery will be monitored by retrieving the defibrillator data download.

2.10 Blinding

2.10.1 Methods for ensuring blinding

It is not possible to blind ambulance staff to treatment allocation as they will see the shock energy when they charge the defibrillator. Patients will be blind to treatment allocation due to the clinical nature of cardiac arrest. Control room staff who allocate ambulance vehicles to emergencies will not be aware of the treatment allocation. It is normal practice for the closest available ambulance to be sent to a cardiac arrest incident. Staff treating participants in hospital may be blind to the patient's treatment allocation since the level of defibrillatory shock is not routinely included in the verbal handover. If patients ask what treatment they received they will be asked not to pass this information to the research paramedic as they should complete the modified Rankin Scale (mRS) assessment blind to the treatment allocation.

2.10.2 Methods for unblinding the study

Since this is an open-label study, no unblinding process will be required.

2.11 Co-enrolment to other studies

Co-enrolment with other trials will be reviewed on a case-by-case basis in accordance with national NIHR-supported co-enrolment guidelines. There are many current examples of successful co-enrolment between UK critical care studies, facilitated by these guidelines.

2.12 End of study

The study will end when all participants have completed their hospital discharge and 30 day follow-ups or after 24 months of patient recruitment, whichever is sooner. Within the last month of recruitment, patients will only be followed up to 30 days to enable timely closure of the study.

The study will be stopped prematurely if:

- Mandated by the Ethics Committee

- Following recommendations from the Study Oversight Committee (SOC)
- Funding for the study ceases

The Research Ethics Committee will be notified in writing within 90 days when the study has been concluded or within 15 days if terminated early. A site study closure plan will be developed and acted upon when the last follow up data have been collected and the data cleaned.

3. METHODS AND ASSESSMENTS

3.1 Schedule of delivery of intervention and data collection

3.1.1 Enrolment

Recruited patients' prehospital data will be taken from routinely collected ambulance service data. Patient and event characteristics, Utstein variables, prehospital treatments and initial outcome will be extracted from the patient clinical record. Call time and ambulance response times will be taken from emergency call centre databases.

Defibrillator data may be attached to the patient clinical record. Alternatively, it will be accessed remotely or directly, if necessary, according to local site constraints. Defibrillator data (treatment summary report) can be downloaded from Zoll X-series devices onto USB devices and viewed via the 'Zoll Code Review/Case Review' software. USB devices may be provided for recording data which may then be sent to the study team.

Enrolments will be identified by research paramedics in one of two ways:

1. Automatic reports generated via the electronic patient record (ePR) system.
2. Searching the Clinical Audit Reporting System (CARS) for paper records.

3.1.2 Hospital

Data from hospital records will be obtained through data-sharing agreements between ambulance services and acute trusts. The research paramedic will liaise with the hospital research team and notify them of each enrolled patient handed over to the hospital. Patients treated for out-of-hospital cardiac arrest are normally taken to the Emergency Department (ED) but may be taken directly to a Coronary Care Unit (CCU) or equivalent for cardiac procedures.

For each patient taken to hospital the following data will be sought:

- Missing demographic data not able to be collected by ambulance service
- Survival status
- Date of admission to ITU/HDU/CCU
- Date of admission to the ward
- Date of discharge (if applicable)

Table 2: Study assessments

	Cardiac arrest	Hospital	Day 30
Inclusion/exclusion criteria	✓	x	x
Cardiac arrest data	✓	x	x
Patient identifiers	✓	✓	x
Adverse event reporting	✓	✓	x

Survival checks	✓	✓	x
Survival status	✓	✓	✓
Notification of enrolment and invitation to take part in follow up	x	✓	x
Informed consent	x	✓	x
Neurological outcome (mRS)	x	x	✓

3.2 Long term follow-up assessments

No long-term follow up shall be conducted in this study. The final data collection point will be at 30 days or at hospital discharge, whichever is later, when the mRS scores of those patients willing to take part shall be assessed. This will usually occur in the hospital but in exceptional cases, if the patient has been discharged prior to this point, may take place at an alternative care facility or in the patient's home.

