The feasibility of assessing the following outcomes for a main trial will be assessed:

- Favourable neurological outcome at discharge and at 30 days (mRS score)
- Return Of Organised Rhythm capable of sustaining a pulse (ROOR) 2 min post (each) shock
- Re-arrest rate (re-fibrillation)
- Survived event (return of spontaneous circulation (ROSC) at hospital handover)
- Survived to hospital discharge and at 30 days

This feasibility study aims to recruit 90 patients, ideally 30 in each arm. This is in keeping with a recommended sample size of at least 50 for feasibility studies.[27]

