difficult to reliably detect in the prehospital setting.[30] ROSC is usually indicated by the manual detection of a carotid pulse. However, when circulation is first re-established the pulse is often weak and healthcare providers have low confidence in their ability to detect weak pulses.[31, 32] In such cases ROSC may be misclassified as Pulseless Electrical Activity (PEA).[33] The in-hospital practice of verifying ROSC using end-tidal carbon dioxide monitoring is not currently routine prehospital practice in the UK.[34] Although possible to confirm ROSC using such monitoring at the time of hospital handover this time point would not provide a pure indicator of shock success due to possible confounding by post-shock treatments.

Return of organised rhythm (ROOR), defined as the detection of two QRS complexes <5s apart, offers a sensitive marker of shock success. Its presence can be assessed by analysis of cardiac rhythm data recorded by defibrillators during guideline-specified pauses in CPR. These pauses occur two minutes post-shock and allow rescuers to analyse a cardiac rhythm in order to determine whether they should deliver a shock. A recent observational study found that these two-minute rhythm checks could provide valuable prognostic information and identified ROOR as the best prognostic marker for survival when compared to VF or asystole.[35] If ROOR is not achieved it may be useful to know the resultant rhythm to assess whether too little (VF/pVT) or too much (asystole) energy may have been delivered and hence which side of the dose-response curve the energy level falls.[36]

The secondary outcomes, survival and neurological function at 30 days, are distal clinical markers of shock success but are the COSCA-recommended outcome measures of resuscitation success.[28] These outcomes can be reported either at discharge or 30 days, in accordance with the Utstein cardiac arrest reporting template, but reporting of a composite outcome (i.e. 'discharge or 30 days') is discouraged. [28, 37] The modified Rankin Scale (mRS) is an adapted version of a scale used to assess level of disability following non-fatal stroke.[38] It is an ordinal scale scoring level of disability from 0 (no symptoms) to 6 (dead) which may be conducted through face to face or telephone interview of the patient or informant.[39] Where this is not possible, trained health professionals may reliably administer the rating through assessment of hospital notes.[39]

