2.7.6 Obtaining consent

Since the study intervention will already have been given at this point, consent will be sought for follow-up i.e. assessment of their neurological status at 30 days and at hospital discharge. Ideally consent will be sought from the patient, or an opinion from their consultee, on the hospital ward. In exceptional cases, when contact has not been made in hospital, if the patient or their consultee responds to the invitation letter a home visit will be arranged during which consent will be sought. Research paramedics shall manage the consent process. The PI shall ensure that appropriate training is provided to ensure that they are competent to fulfil this delegated responsibility.

The consent form will explicitly list all of the activities and data sources for which consent is sought, allowing the option to choose those for which consent is granted. Data already collected prior to the meeting will be retained unless explicit consent for its use is denied.

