Information requests for patients not known to have died will be sent to the appropriate research team at the destination hospital. Information sought will include patient identifiers that the ambulance staff may have been unable to obtain, including survival status, patient location and date of transfer to the hospital ward. This will be sought by completion of a spreadsheet and will be sent securely via nhs.net email system. Ongoing checks regarding patient location and survival status will be made in order that a visit may be arranged at the appropriate time. Personal identifiers will only be shared between those in the direct care team, i.e. the ambulance service and the destination hospital, and not with the WCTU.

The mRS scores of surviving patients will be assessed at 30-days post event by the research paramedics using the Rankin Focussed Assessment (RFA) tool. This tool has excellent inter-observer reliability (unweighted κ of 0.93 (95% CI, 0.85-1.00)).[47] At 30 days, patients may have been

discharged home or they may be on the hospital ward. We will arrange to visit patients in either location to assess mRS. If the patient has been discharged home, two survival checks will first be made before telephoning the patient. Assessing mRS when they have been discharged into their home setting allows patients to accurately assess their abilities regarding their normal activities.[28] However, since the RFA encourages the gathering of information from all available sources it may also be reliably applied in the hospital setting.[47] Should the patient lack capacity at 30 days and remain in hospital the RFA will be completed with the consultee, nursing staff and the medical notes. Should they be at home, the opinion of the patient's consultee will be sought to complete the RFA. Where a proxy is required for mRS assessment, family members have been found to be more reliable than nurses or therapists.[48] A lone working risk assessment shall be carried out in accordance with the Warwick SOP. Home visits shall be carried out within office hours and within daylight hours where possible. Research paramedics shall ensure that they inform a member of the study team prior to entering an address, carry a mobile phone and undertake a dynamic risk assessment during the visit and inform the study team on leaving the address.

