6.2.3.3 Secondary outcome analysis

The secondary outcomes that will be assessed are:

- Treatment adherence rate. This will be assessed in terms of how many patients received the allocated first shock energy and, where more than one shock was delivered, how many received the correct subsequent shock energies.
- Data completeness of clinical outcomes below:
 - Neurologically intact survival at 30 days and hospital discharge (mRS score)
 - Return Of Organised Rhythm (ROOR) 2 min post shock

- Resulting rhythm (VF/pVT/PEA/asystole) 2 min post shock
- Re-arrest rate (re-fibrillation)
- Survived event (return of spontaneous circulation (ROSC) at hospital handover)
- Survived to hospital discharge and 30 days

These will be reported in terms of the proportion of patients for whom each of these outcomes was collected.

- Data completeness of process outcomes below:
 - Quality of CPR (chest compression rate, chest compression depth, chest compression fraction, pre-shock pause, post-shock pause)
 - Number of shocks
 - Advanced airway applied (% advanced airway applied and % supraglottic airway or endotracheal tube)
 - Intravenous medicines administered (% cases where medicines administered and % adrenaline, amiodarone)
 - Transported to hospital (% transported)
- Issues identified by ambulance staff and suggestions for study optimisation. These will be reported in terms of the topics identified, with example anonymised quotes, from the thematic analysis of the focus group data.
- Acceptability of approach to informing relatives of non-survivors. We will monitor the number and nature of enquiries received by the Ambulance Service, the time taken to identify next of kin, the sources consulted to verify next of kin details and the concordance/discordance between different sources.

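### mRS at discharge and at 30 days are reported as two outcomes, but the schedule provides only one assessment per survivor, so discharge-mRS completeness would partly reflect the schedule

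*Protocol*

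**What the plan says.** Four places in the protocol promise two time points:

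- Section 2.1 lists, among the outcomes whose feasibility is to be assessed, "Favourable neurological outcome at discharge and at 30 days (mRS score".
- Table 1 (2.3.2) gives neurological function both time points, with the patient and/or clinical records as source and a research paramedic or GP as assessor.
- Section 2.7.6 says "consent will be sought for follow-up i.e. assessment of their neurological status at 30 days and at hospital discharge".
- Section 6.2.3.3 lists "Neurologically intact survival at 30 days and hospital discharge (mRS score" among the outcomes whose completeness is reported, as the share of patients for whom each was collected.

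The operational text differs:

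- In Table 2 (3.1.2), the row "Neurological outcome (mRS" has a cross under Cardiac arrest and under Hospital, and a tick only under Day 30. The hospital data list in the same section asks for survival status and dates, but not for mRS.
- Section 5.1 says "The mRS scores of surviving patients will be assessed at 30-days post event by the research paramedics".
- The follow-up alert in 6.5 is triggered only at 30 days, and 1.5.5 describes follow-up through a consultee as 30 days only.
- Section 3.2 says "The final data collection point will be at 30 days or at hospital discharge, whichever is later, when the mRS scores of those patients" who agree to follow-up are assessed.

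Section 2.3.2 adds that "reporting of a composite outcome (i.e. 'discharge or 30 days') is discouraged".

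**The concern.** In this study, completeness is itself the result. One secondary objective (2.2.2) is to identify the best outcome measures for a main trial by looking at how completely each was recorded. If staff are told to report on a discharge score but are never scheduled to obtain one, a low figure says something about the schedule and little about whether the score can be collected. A statistical analysis plan cannot repair this afterwards, because it cannot recover assessments that nobody was prompted to make.

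Section 3.2 raises a second difficulty. One assessment at the later of two dates gives a score at day 30 for some survivors and at discharge for others. Neither time point is then observed in all survivors, and pooling the scores would come close to the mixed outcome that 2.3.2 advises against.

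**Working it through.** **Step 1. The passages side by side.** For each type of survivor, the mRS assessments called for are:

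| Text followed | Discharged before day 30 | Still in hospital at day 30 |
|---|---|---|
| 2.1, Table 1, 2.7.6, 6.2.3.3 | discharge and day 30 | day 30 and discharge |
| Table 2 and 5.1 | day 30 only | day 30 only |
| 3.2 | day 30 only | discharge only |

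No two rows agree, and no other section settles which applies. For survivors discharged before day 30, neither operational version plans a discharge score. For those still in hospital, the two operational versions contradict each other.

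**Step 2. Number of survivors.** Inputs: 90 patients (6.1); 20.9% survival to discharge in initially shockable rhythm (1.1); 7.2% in non-shockable rhythm (1.5.1). Expected survivors = 90 × survival.

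- 90 × 0.209 = 18.8, about 19.
- 90 × 0.072 = 6.5, so 6 to 7.

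Section 2.1 also admits patients whose shockable rhythm came later in the arrest, so 19 lies near the upper end.

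**Step 3. Discharge-mRS completeness among survivors.** Under Table 2 and 5.1 it is 0/19 = 0%. Under 3.2, only survivors discharged after day 30 have a discharge score, so completeness = (19 − number discharged before day 30)/19. The protocol does not give the share discharged before day 30. It is assumed here to be 50–100%, with counts rounded to whole patients.

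| Assumed share out before day 30 | Without planned discharge mRS | Discharge completeness, survivors | Day-30 completeness, survivors (3.2) | Discharge completeness, all 90 |
|---|---|---|---|---|
| 50% | 10 | 9/19 = 47% | 10/19 = 53% | 80/90 = 89% |
| 70% | 13 | 6/19 = 32% | 13/19 = 68% | 77/90 = 86% |
| 90% | 17 | 2/19 = 11% | 17/19 = 89% | 73/90 = 81% |
| 100% | 19 | 0/19 = 0% | 19/19 = 100% | 71/90 = 79% |

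Under 3.2 each survivor has exactly one score, so the two survivor columns add to 100% whatever the share. A gain at one time point is a loss at the other.

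**Step 4. All-patient figure.** The last column is (90 − number without planned discharge mRS)/90. It counts every death as a known score of 6, the value that 2.3.2 gives to death. Under Table 2 and 5.1 it is 71/90 = 79%. With 6.5 survivors, its lowest value would be (90 − 6.5)/90 = 93%. A figure of this size could be reported with no discharge score at all among survivors.

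**The case against.** The strongest case on the other side has four parts.

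- **Table 1 already provides for the discharge score.** It names a time point, a source and an assessor, and 2.7.6 brings the score within the consent. This stands in part: the score could be recovered from notes. But 2.3.2 offers scoring from notes only where interview is not possible, and no section prompts that extraction at discharge.
- **The wording in 3.2 may only define the last contact.** That reading is possible, but the same sentence ties the mRS assessment to that point. Section 3.2 also expects the assessment to take place usually in hospital. If so, the share discharged before day 30 could be below 50%, and discharge completeness under 3.2 above 47%. That is a fair limit on the range, but under 3.2 the day-30 gap then widens by the same amount.
- **Section 2.3.2 discourages reporting a composite, and 6.2.3.3 lists two time points.** This stands. Section 3.2 would produce scores at mixed time points, but nothing says that they will be reported as one outcome.
- **This is one time point of one secondary item** in a study with no formal analysis (6.2.1). This also stands and limits the severity.

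A reader might also infer that 2.12, which can end the study "after 24 months of patient recruitment, whichever is sooner", cuts off the 30-day follow-up of the last recruits. The timetable in 7.6 does not support that. Recruitment runs over months 4–24 (24 − 4 + 1 = 21 months) and follow-up ends in month 25. Twenty-four months of recruitment from month 4 would end in month 27 (4 + 24 − 1), so on that timetable the limit does not bind.

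**Conclusion.** The inconsistency is real and unresolved. Four places define two mRS outcomes, while Table 2 with 5.1, and separately 3.2, each provide for one assessment per survivor. Up to about 19 of 90 patients are concerned at 20.9% survival, and 6 to 7 at 7.2%. With 19 survivors, discharge completeness among survivors is 0% under Table 2 and 5.1, and 0–47% under 3.2 on the assumption that 50–100% leave before day 30. The all-patient figure would read about 79–89%, if deaths count as a score of 6.

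A reader might infer that discharge mRS will be almost wholly missing and then be wrongly rejected for the main trial. The protocol does not support going that far. The 0% figure follows only from Table 2 and 5.1, or from every survivor leaving before day 30. Table 1 leaves a records-based route open, 6.5 requires reasons for unobtainable data to be recorded, and no decision threshold is attached to mRS completeness.

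This should be fixed. It is a correction of internal consistency and does not touch the primary feasibility outcome or the adherence outcome.

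**What to change.** Reconcile Table 1, Table 2, 3.2, 5.1, 6.5 and 6.2.3.3 in one of two ways.

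1. **Keep both time points.** Add a separately recorded discharge mRS to the hospital column of Table 2 and to 5.1, taken from the patient or, where interview is not possible, from records. Add a discharge prompt to 6.5. Reword 3.2 as two assessments, neither of which substitutes for the other.
2. **Keep day 30 only.** Delete discharge mRS from 2.1, Table 1, 2.7.6 and 6.2.3.3, and reword 3.2 to match.

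In either case, report mRS completeness among survivors beside the all-patient figure, and state whether deaths count as a collected score of 6. Record the date to which each score refers. The discharge date is already sought under 3.1.2, so scores already taken can be assigned to the right time point.

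The first option costs a small amount of extra scoring by the existing research paramedics, for at most about 19 survivors. The second costs only wording, but the study would then say nothing about collecting mRS at discharge.
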